In the equation above, the factor for "Sex" equals 0.85 for females and 1 for males

2.1.1.10 The effects of enzalutamide alone or in combination with PSA-TRICOM on the developing human fetus are unknown. For this reason, men must agree to use adequate contraception (hormonal or barrier method of birth control; abstinence) prior to study entry, for the duration of study participation and for three (3) months after the last dose of enzalutamide. Should a woman become pregnant or suspect she is pregnant while her partner is participating in this study, she should inform her treating physician immediately.

2.1.1.11 Ability of subject to understand and the willingness to sign a written informed consent document.

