3.6 CRITERIA FOR REMOVAL FROM PROTOCOL THERAPY AND OFF STUDY CRITERIA

3.6.1 Criteria for removal from protocol therapy

- Disease progression as evidenced by radiographic or clinical progression (defined in section [5.3.5](#)).
- Intercurrent illness or medical circumstances: if at any time the constraints of this protocol are detrimental to the patient's health, the patient may be removed from protocol therapy. In this event, the reasons for withdrawal will be documented.
- Patient's request to be taken off study. In this event, the reasons for withdrawal will be documented.
- If patients are non-compliant with the protocol guidelines, they may be removed from the study at the discretion of the principal investigator.
- Any Grade 4 toxicity that is possibly, probably or definitely related to the protocol treatment will require a patient to be off-treatment.
- Grade ≥ 3 autoimmune toxicity while on vaccine, will require a patient to be off-treatment.
- Any Grade 3 non-autoimmune toxicity that does not resolve to Grade 1 or baseline within 60 days and is possibly, probably or definitely related to the protocol treatment will require a patient to be off-treatment.
- Any grade of seizure will require discontinuation of enzalutamide but patients may continue vaccine at the discretion of the investigator.

Prior to documenting removal from protocol therapy, effort must be made to have all subjects complete a safety visit approximately 30 days following the last dose of study therapy.

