7.6.1 Paternal Exposure

Male patients should refrain from fathering a child or donating sperm during the study and for three (3) months after the last dose of enzalutamide.

Pregnancy of the patient's partner is not considered to be an AE. However, the outcome of all pregnancies (spontaneous miscarriage, elective termination, ectopic pregnancy, normal birth, or congenital abnormality) occurring from the date of the first dose until three (3) months after the last dose should, if possible, be followed up and documented.

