13.1.2 Patient Care Implications and Contraindications

Cover vaccination sites with a sterile dry dressing (e.g., Telfa pad). Once the injection site is healed, no further barrier is necessary. As a precaution, protect injection sites that are exhibiting evidence of weeping, oozing or ulceration with a sterile dry dressing. In these circumstances, instruct patients to avoid direct contact of the injection site with susceptible individuals (e.g.; those who may be immunocompromised by disease or therapy). Instruct patients to avoid fathering a child for at least 4 months following therapy completion with the recombinant vaccine. Instruct patients receiving fowlpox vaccines to avoid direct contact with pet birds for at least 72 hours after vaccination or while there are any visible lesions at the injection site.

Due to the method of manufacturing (virus grown in primary chicken embryo dermal cells), patients with a history of allergy to eggs or egg products should not receive the vaccine.

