13.2.10.1 Patient Care Implications and Contraindications

Cover vaccination sites with a sterile dry dressing (e.g., Telfa pad). Instruct patients on proper hand-hygiene, sterile dressing care, bathing, laundering of clothing, etc. Treat patient bandages or dressings removed from the vaccination site as infectious waste and dispose in appropriate biohazard containers. Do not administer the recombinant vaccinia vaccine if the recipient, or for at least three weeks after

vaccination, their close household contacts (close household contacts are those who share housing or have close physical contact):

- have active eczema or a history of eczema or atopic dermatitis, or Darier's disease.
- have other acute, chronic, or exfoliative skin conditions (e.g., burns, impetigo, varicella zoster, severe acne, contact dermatitis, psoriasis, herpes or other open rashes or wounds), until the condition resolves.
- are pregnant or intend to become pregnant (due to the potential risk of fetal vaccinia); or are breast-feeding (due to the potential risk of contact transmission and inadvertent inoculation). It is currently unknown if vaccinia virus or antibodies are excreted in breast milk. Patients (i.e., vaccinees) should avoid fathering a child for at least 4 months following completion of therapy with the recombinant vaccine.
- are in close contact with children less than 3 years of age (due to the potential risk of contact transmission and inadvertent inoculation).
- are immunodeficient or immunocompromised (by disease or therapy), including individuals with HIV infection.

Additionally, do not administer the recombinant vaccinia vaccine if the vaccinee:

- has a moderate or severe acute illness, until the illness resolves.
- is undergoing topical steroid therapy for inflammatory eye diseases, or undergoing therapy with systemic steroids; potential immune suppression increases risk for vaccinia-related complications.
- At this time, until a more definitive causal relationship is determined, it is recommended that patients with known CHF or clinically significant cardiomyopathy, not be vaccinated with recombinant vaccinia-based vaccines, due to the potential for development of myocarditis and/or pericarditis.

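### For Arm B, the 3-month post-enzalutamide window (2.1.1.10, 7.6.1) and the 4-month post-vaccine window (13.1.2, 13.2.10.1) are not reconciled, and the pregnancy-outcome window names no product

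*Combined protocol and SAP*

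**What the plan says.** Two sections count from enzalutamide and make no distinction between arms. Section 2.1.1.10 opens by saying that the fetal effects of enzalutamide, alone or with PSA-TRICOM, are unknown. It then sets contraception "for the duration of study participation and for three (3) months after the last dose of enzalutamide". Section 7.6.1 tells men to "refrain from fathering a child or donating sperm during the study and for three (3) months after the last dose of enzalutamide".

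Two sections count from the vaccine. Section 13.1.2 (fowlpox) reads: "Instruct patients to avoid fathering a child for at least 4 months following therapy completion with the recombinant vaccine". Section 13.2.10.1 (vaccinia) says that vaccinees "should avoid fathering a child for at least 4 months following completion of therapy with the recombinant vaccine".

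Section 7.6.1 also sets the period for following partner pregnancies: those "occurring from the date of the first dose until three (3) months after the last dose". This sentence does not say which product's last dose is meant.

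One rule can make the vaccine outlast enzalutamide. Section 3.6.1 states: "Any grade of seizure will require discontinuation of enzalutamide but patients may continue vaccine at the discretion of the investigator". Under 3.6.2 a man goes off study once he is off treatment and has had a visit at about 30 days, where feasible.

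**The concern.** The two pairs of sections differ in both length and starting point, and neither pair refers to the other. A man in Arm B can keep to his entry agreement and to 7.6.1 and still be inside the period in which the vaccine sections tell him not to father a child. A pregnancy conceived then may also fall outside the outcome window of 7.6.1. The record of partner exposure could therefore be incomplete in the only arm that receives a viral-vector vaccine. No efficacy analysis is affected; the issue is participant instruction and completeness of safety data.

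**Working it through.** The plan states no figure to reproduce, so the check is date arithmetic. One month is taken as 365.25/12 = 30.4 days, which makes 3 months 91.3 days and 4 months 121.75 days.

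**Ordinary stop.** Let g be the days from the last vaccine to the last enzalutamide dose (g ≥ 0). Counted from the last vaccine, the enzalutamide-based window ends at day g + 91.3 and the vaccine-section period at day 121.75.

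Shortfall = max(0, 121.75 − (g + 91.3)) = max(0, 30.4 − g) days.

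| g (days) | Shortfall (days) |
|---|---|
| 0 | 30.4 |
| 14 | 16.4 |
| 28 | 2.4 |
| 30.4 or more | 0 |

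**Stops at scheduled scans.** From 3.1 and the study calendar (3.4), vaccine falls at weeks 1, 3, 5, 9, 13, 17, 21, 33, 45, 57 and 69. After one 10-week interval it falls at week 79 and then every 12 weeks. Scans fall at weeks 13, 25, 37, 49, 61 and 73, then at 85, 97 and so on. Suppose both products stop at an on-time scan and no vaccine is given that day.

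- Scans at weeks 13 to 73: the last vaccine was 28 days earlier, so the shortfall is 30.4 − 28 = 2.4 days.
- Scans from week 85: the last vaccine was 42 days earlier, so the enzalutamide-based window ends at about day 133 and there is no shortfall.

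**Departures from that pattern.** Section 3.3.3.5 lets a vaccine dose missed for scheduling or logistical reasons be given within 14 days. That cuts a 28-day gap to 14 and raises the shortfall to about 16 days. Week 13 is both a vaccine and a scan week, so vaccine may be given before progression is read; g is then near 0 and the shortfall near 30 days. Clinical progression, toxicity or patient request (3.6.1) can stop treatment on any date. Footnote 2 of the calendar lets long-term patients move to 12-week visits with vaccine shifted to fit, so vaccine and scan may share a visit.

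**Seizure, vaccine continued.** Let d be the days from the last enzalutamide dose to the last vaccine. Study participation still covers the man until about 30 days after the last vaccine, assuming the 3.6.2 visit takes place.

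Cover after the last vaccine under 2.1.1.10 = max(30, 91.3 − d) days.

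- d = 30: cover 61.3 days, shortfall 121.75 − 61.3 = 60.4 days.
- d of about 61 or more: cover 30 days, shortfall 121.75 − 30 = 91.8 days, or about 3 months.

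Expected number: section 13.4.6.1 reports seizure in 7 of 800 men (0.9%). Applied to 36 men in Arm B, 36 × 7/800 = 0.3. This is the number with a seizure; those who then continue vaccine can only be fewer.

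**Pregnancy-outcome window.** If the final dose means that of either product, the shortfall is max(0, 30.4 − g) when enzalutamide ends last and 30.4 days when vaccine ends last, so never more than about 1 month. If it means enzalutamide only, and vaccine continued, the shortfall is 30.4 + d, since this sentence has no study-participation floor. At d = 90 it is 120.4 days, nearly the whole 4 months.

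**Which vaccine.** Vaccinia is given once, in week 1 (3.1). Four months from that dose ends at about day 122. The enzalutamide-based window reaches that day for any man who takes enzalutamide for about 122 − 91 = 31 days or more. The continuing gap therefore mainly concerns the repeated fowlpox doses.

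**The case against.** The strongest reply is that the rules add to each other. One runs from enzalutamide, the other from vaccine, and a man can keep both. The 4-month instruction is in this protocol, so the inference that Arm B men have no such instruction is not supported. What stands is that the entry agreement and the reporting section do not carry it.

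A reader might infer that Arm B men generally leave the window early. The documents do not support this: with daily enzalutamide and 12-weekly vaccine, anyone stopping enzalutamide more than about a month after his last vaccine is covered for the full 4 months. Spreading stop dates evenly over an 84-day vaccine interval would give a shortfall on 31/84 = 37% of days, but nothing in the plan supports even spacing when treatment runs to progression and scans follow a fixed calendar. Because some stops are not tied to scans, the true frequency cannot be derived from the documents.

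A reader might also take pregnancy follow-up as tied to enzalutamide. The sentence names no product, so that is one reading of two. Nor is there a continuing gap for the replication-competent vaccinia vector in nearly all men; section 13.1 describes fowlpox as unable to replicate outside birds.

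Practical reach is limited. Accrual had closed by 12/20/2016 (6.5.2) and this version is dated March 2022, so 2.1.1.10 binds no new entrant, and men still on treatment are long past the 4-weekly vaccine phase. All have castrate testosterone and continue androgen deprivation or have had orchiectomy. The documents give no partner-pregnancy rate. These points lower the severity; they do not remove the inconsistency, because 7.6.1 still applies to men on treatment.

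**Conclusion.** The inconsistency is real and minor. It opens only when the last vaccine is less than about 1 month before the last enzalutamide dose, or when vaccine outlasts enzalutamide after a seizure. The sizes shown rest on a 30.4-day month. The scan-based results also assume on-time visits. The seizure results assume the roughly 30-day visit in 3.6.2 and a seizure rate carried over from the randomized trial in 13.4.6.1.

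The pregnancy-outcome window is at once ambiguous and, on either reading, capable of closing before the vaccine-section period does. Confidence is medium: Appendix B (the vaccinia patient instruction sheet) and the consent text were not available, and either may already tell Arm B men which period applies. The documents do not establish which period is right, and no view is taken on that.

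**What to change.** Reconcile 2.1.1.10 and 7.6.1 with 13.1.2 and 13.2.10.1 for Arm B. Either a single period or explicit product-specific periods would do, provided each states the product and dose from which it runs. The text should cover a man who stops one product and continues the other, as 3.6.1 allows after a seizure. In 7.6.1, name the product whose last dose anchors the pregnancy-outcome window, and make that window cover the reconciled period. Check Appendix B and the consent form against the result. The clinical team decides the period.

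The cost is amendment wording, consent wording if that check shows it is needed, and at most a slightly longer pregnancy-outcome enquiry for Arm B men. No endpoint, sample size or analysis changes.

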2.1.2 Exclusion Criteria

2.1.2.1 Patients who are immunocompromised as listed as follows:

- Human immunodeficiency virus positivity due to the potential for decreased tolerance and may be at risk for severe side effects
- Chronic administration (defined as daily or every other day for continued use >14 days) of systemic corticosteroids (including steroid eye drops) or other immune suppressive drugs, within 28 days before the first planned dose of PSA-TRICOM. Nasal, or inhaled steroid, and topical steroid creams for small body areas are not excluded.
- Patients who have undergone allogeneic peripheral stem cell transplantation, or solid organ transplantation requiring immunosuppression
- History of splenectomy

2.1.2.2 History of, or active autoimmune disease (such as Autoimmune neutropenia, thrombocytopenia, or hemolytic anemia, systemic lupus erythematosus, Sjogrens syndrome, scleroderma, myasthenia gravis, Goodpasture's syndrome, Addisons disease, Hashimotos thyroiditis, Crohns or Graves disease). Patients with type 1 diabetes

mellitus or vitiligo are not excluded if the condition is well controlled.

- 2.1.2.3 Patients with a history of brain/leptomeningeal metastasis
- 2.1.2.4 Patients who have been treated with abiraterone will be excluded
- 2.1.2.5 Patients with history of seizure as an adult including febrile seizure or any condition that may predispose to seizure (e.g., prior stroke, brain arteriovenous malformation, head trauma with loss of consciousness requiring hospitalization). Also, current or prior treatment with anti-epileptic medications for the treatment of seizures or history of loss of consciousness. Also transient ischemic attack within 12 months prior to randomization will not be permitted.
- 2.1.2.6 Patients with second malignancy within 3 years of enrollment; Patients curatively treated non-melanoma skin cancers or carcinoma in situ of the bladder, are not excluded.
- 2.1.2.7 History of allergic reactions attributed to compounds of similar chemical or biologic composition to *enzalutamide* or poxviral vaccines (e.g., vaccinia vaccine)
- 2.1.2.8 Known allergy to eggs, egg products, aminoglycoside antibiotics (for example, gentamicin or tobramycin),
- 2.1.2.9 History of atopic dermatitis or active skin condition (acute, chronic, exfoliative) that disrupts the epidermis
- 2.1.2.10 Previous adverse reactions to smallpox vaccination
- 2.1.2.11 Unable to avoid close contact or household contact with the following high-risk individuals for three weeks after the Day 1 vaccination: (a) children \leq 3 years of age, (b) pregnant or nursing women, (c) individuals with prior or concurrent extensive eczema or other eczemoid skin disorders, or (d) immunocompromised individuals, such as those with HIV.
- 2.1.2.12 Any condition which, in the opinion of the investigator, would prevent full participation in this trial (including the long-term follow-up), or would interfere with the evaluation of the trial endpoints.
- 2.1.2.13 Patients with prior chemotherapy for nonmetastatic prostate cancer within a year are excluded.
- 2.1.2.14 Receipt of an investigational agent within 28 days (or 56 days for an antibody-based therapy) before the first planned dose of study drugs. (Immune checkpoint inhibitors that are antibody-based will only require 28 days before enrollment)
- 2.1.2.15 Uncontrolled intercurrent illness including, but not limited to, ongoing or active infection, symptomatic congestive heart failure, unstable angina pectoris, cardiac arrhythmia, uncontrolled hypertension (SBP $>$ 170/ DBP $>$ 105) or psychiatric illness/social situations within 12 months that would limit compliance with study requirements.
- 2.1.2.16 Use of herbal products that may decrease PSA levels (e.g. saw palmetto)
- 2.1.2.17 Any gastrointestinal disease that could hinder the absorption of enzalutamide.
- 2.1.2.18 Patients who have had chemotherapy for metastatic castration-resistant prostate cancer. (Patients who have had docetaxel for metastatic castration sensitive disease per CHAARTED Data[34] may enroll as long as they did not have progressive disease

Short Title: Enzalutamide Vaccine in mCRPC

Version Date: 03/29/2022

while on docetaxel and are 6 months removed from treatment, with all treatment related toxicities resolving to at least grade 1.)

2.1.2.19 Patients who have received radiation therapy, radionuclide therapy or undergone surgery within certain duration (4 weeks) of enrollment

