2.3.1 Treatment Assignment and Randomization/Stratification Procedures

Cohorts

Number	Name	Description
1	Prostate Cancer Patients	Patients with chemotherapy naïve metastatic castrate-resistant prostate cancer

Short Title: Enzalutamide Vaccine in mCRPC

Version Date: 03/29/2022

Arms

Number	Name	Description
1	A	Enzalutamide alone
2	B	Enzalutamide with PSA-TRICOM

Stratifications

Name	Distinct Options	Notes
Prior Immunotherapy	Yes No	

Randomization and Arm Assignment

Patients must be registered with Central Registration Information Services within 24 hours after signing the consent. All Patients on study will be directly assigned to cohort 1.

Patients in cohort 1 will be randomized within 24 hours after registration. Block randomization will be used to randomly assign patients in a 1:1 manner between arms A and B. Randomization will be stratified by prior immunotherapy used as cancer treatment.

For randomization, authorized staff should call [contact] between the hours of 8:30 a.m. and 5:00 p.m., Monday through Friday. A recorder is available during non-working hours.

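### The entry criteria admit some men whom the product section bars from vaccinia, so the conflict surfaces after randomisation and in Arm B only

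*Combined protocol and SAP*

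**What the plan says.** Three entry criteria in section 2.1.2 bear on the safety of vaccinia.

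- **Contacts (2.1.2.11).** A man is excluded if "Unable to avoid close contact or household contact with the following high-risk individuals for three weeks after the Day 1 vaccination". The list covers young children, pregnant or nursing women, immunocompromised people and, for skin disease, "c) individuals with prior or concurrent extensive eczema or other eczemoid skin disorders".
- **The patient's own skin (2.1.2.9).** The exclusion is "History of atopic dermatitis or active skin condition (acute, chronic, exfoliative) that disrupts the epidermis".
- **Steroids (2.1.2.1).** The exclusion is "Chronic administration (defined as daily or every other day for continued use >14 days) of systemic corticosteroids (including steroid eye drops", counted over the 28 days before the first planned vaccine dose.

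Section 13.2.10.1 is a prohibition on giving vaccinia. It applies to the recipient and, for at least three weeks after vaccination, to close household contacts. It covers active or past eczema or atopic dermatitis, and Darier's disease. It also applies to those who "have other acute, chronic, or exfoliative skin conditions (e.g., burns, impetigo, varicella zoster, severe acne, contact dermatitis, psoriasis" and similar, until resolved, and to those who "are pregnant or intend to become pregnant (due to the potential risk of fetal vaccinia". For the recipient alone it adds a man who "is undergoing topical steroid therapy for inflammatory eye diseases, or undergoing therapy with systemic steroids", with no minimum duration.

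On timing, section 2.3.1 says "Patients in cohort 1 will be randomized within 24 hours after registration". Section 3.1 gives vaccinia once, in week 1, and only men allocated to Arm B receive it.

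**The concern.** If the entry list is narrower than the administration list, a man can satisfy every written criterion, be randomised to Arm B, and only then meet a stated bar to his first vaccine dose. There are two ways out. Either he is vaccinated and he or a contact is exposed against section 13, or the priming dose is delayed or withheld. Nothing comparable can happen in Arm A. The first outcome is a safety and compliance matter. The second is a departure from assigned treatment that arises after allocation in one arm only. If such men were then dropped or replaced, the randomised comparison would lose its protection.

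**Working it through.** The point rests on no figure in the plan, so the check is a line-by-line comparison.

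| Topic | Entry rule (2.1.2) | Product rule (13.2.10.1) | Who falls between |
|---|---|---|---|
| Patient, past skin disease | History counts for atopic dermatitis only (2.1.2.9) | Any history of eczema | Past non-atopic eczema |
| Patient, Darier's disease | Counts only if active and breaching the epidermis (2.1.2.9) | Named without qualifier | Quiescent Darier's disease |
| Patient, other skin conditions | Active and breaching the epidermis (2.1.2.9) | Listed conditions, including psoriasis and contact dermatitis, until resolved | Psoriasis or similar with intact epidermis |
| Contact, eczema | Extensive eczema or eczemoid disorders (2.1.2.11) | Any active or past eczema | Contact with non-extensive eczema |
| Contact, other skin conditions | Not listed | Burns, impetigo, zoster and others, until resolved | Contact with any of these |
| Contact, pregnancy | Pregnant or nursing (2.1.2.11) | Also intending pregnancy | Contact who intends pregnancy |
| Patient, steroids | Daily or alternate-day use beyond 14 days, eye drops included (2.1.2.1) | Any current systemic steroid, or topical steroid for inflammatory eye disease | Current use of 14 days or less |

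I then looked for text elsewhere that closes the gap.

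1. Section 2.1.2.12 allows exclusion for conditions that the investigator thinks would prevent full participation. It can be used for these men, but it is discretionary and does not refer to 13.2.10.1.
2. Section 2.1.2.15 excludes uncontrolled intercurrent illness, including active infection. It would catch the patient's own impetigo or zoster. It does not reach a contact's condition or a short steroid course.
3. Section 3.3.3.5 allows a vaccine dose to move by up to 14 days, but only for scheduling or logistical reasons. No rule covers a day-1 dose that is contraindicated.
4. Nothing in section 2 makes eligibility depend on the 13.2.10.1 list.
5. Appendix B, the vaccinia patient instruction sheet, appears in the table of contents but was not available for review. It may give advice about contacts; an instruction sheet would not by itself change who is eligible.

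Each of the three areas (skin, contacts, steroids) therefore contains at least one condition that section 2.1.2 admits and 13.2.10.1 prohibits. The conflict arises after allocation because only Arm B receives vaccinia.

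**The case against.** The gap is smaller than a quick reading suggests, and most of the case for that stands.

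- **The patient's own active disease is largely covered.** Sections 2.1.2.9 and 2.1.2.15 together catch most open or infected skin. What remains is past non-atopic eczema, quiescent Darier's disease and conditions with intact epidermis.
- **Some bars are temporary.** The general skin-condition bar ends on resolution and the steroid bar ends with treatment, so a dose may be delayed rather than lost. The bars for eczema history and Darier's disease carry no such end point.
- **An investigator would probably notice.** History and examination are done within 30 days before enrolment, so randomising within a day of registration does not prevent detection. But detection depends on the investigator going beyond the written criteria.
- **Accrual is over.** Section 6.5.2 dates closure to 12/20/2016, and this version is from March 2022. Changing the entry wording cannot alter who was enrolled.

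Two stronger readings do not hold. A reader might infer that entry is looser throughout. It is not: the entry rule covers children up to and including 3 years where the product section says under 3, and its 28-day look-back for chronic steroids is the stricter of the two. The three-week contact window is broadly the same in both places. A reader might also infer that the steroid rule cannot apply to Arm A because it counts back from the first PSA-TRICOM dose. But the text refers to a planned dose and is applied before allocation, when any candidate may be assigned vaccine, so it works for both arms.

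**Conclusion.** The two sections contradict each other for an identifiable set of men, and the consequence falls on Arm B alone. That much rests only on the wording. Whether any enrolled man was affected is not known from the documents, and discretionary exclusion under 2.1.2.12 may have kept the number at zero.

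A reader might infer a definite loss of power. Schoenfeld's formula, power = Φ(½√52 × ln HR − 1.282), gives 79.9% at the plan's 52 events and hazard ratio of 1.80, which matches its stated 80%. Suppose k of 36 Arm B men gained nothing from assignment and the log hazard ratio shrank in proportion, so that HR = 1.80^(1 − k/36). Then k = 1, 2 or 4 gives hazard ratios of 1.771, 1.742 and 1.686, and power of 78.2%, 76.4% and 72.7%. The documents do not support using these as an estimate. They give no value for k. They also do not establish that such men would go wholly without vaccine: the fowlpox section (13.1.2) has no matching bar on administration for eczema, contacts or steroids, and the protocol does not say whether boosters proceed without the priming dose.

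A reader might also infer that these men would use up the allowance for inevaluable patients in section 9 (76 enrolled for 72 evaluable, a margin of 4). That does not follow. They would still receive enzalutamide. Section 5.3.2, writing about response, makes a possible exception only for men who received no study medication, and says that incorrect administration is no ground for exclusion. Section 9 does not define inevaluable, so the treatment of these men should be stated rather than left open.

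**What to change.** **For the men already enrolled.** Review the records, and report by arm any man whose day-1 vaccinia was withheld, delayed or given despite a condition listed in 13.2.10.1. State that all of them stay in the primary time-to-progression analysis as randomised and are not treated as inevaluable.

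**For the document, and for any further enrolment or successor use.** Reconcile 2.1.2.1, 2.1.2.9 and 2.1.2.11 with 13.2.10.1 into one list, applied to every candidate before allocation. Which conditions and thresholds belong on it is for the clinical team to decide. Check Appendix B against the same list.

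**Cost.** A small record review and some amendment wording. Neither changes the sample size or the planned test.
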